7.3 Study Monitoring

The investigator will be visited on a regular basis by the Clinical Study Monitor, who will check the following:

- Informed consent process
- Reporting of adverse events in the HAI-treatment arm and all other safety data

- Adherence to protocol
- Maintenance of required regulatory documents
- Data completion on the CRFs including source data verification (SDV).

The monitor will review the relevant CRFs for accuracy and completeness in accordance with monitoring plan and will ask the site staff to adjust any discrepancies as required.

Sponsor's representatives (e.g. monitors, auditors) and/or competent authorities will be allowed access to source data for source data verification in which case a review of those parts of the hospital records relevant to the study will be required.

7.4 Confidentiality

The investigator shall arrange for the secure retention of the patient identification and the code list. Patient files shall be kept for the maximum period of time permitted by each hospital. The study documentation (CRFs, Site File etc) shall be retained and stored during the study and for 15 years after study closure. All information concerning the study will be stored in a safe place inaccessible to unauthorized personnel.

8 STATISTICAL METHODS AND DATA ANALYSIS

8.1 Determination of Sample Size

We estimate an overall survival at two years in the standard care group (group 3) to be 30 %. We aim to decide whether the use of HAI (group 2) can increase this to 75 % and if liver-TX (group 3) can increase this to 90 %. For a two-sided parallel-group test of proportions to answer both questions with a power of 0.80 and an alpha of 0.05, this will require 16 completed patients per group 3 and 2 to show superiority for HAI over standard care (systemic chemotherapy). An additional 7 patients is needed in the transplant group (1) to show superiority over standard care group (3), bringing the total to 39 patients. This is based on a three-year accrual time, and a total of five-year follow-up from the first patient, ensuring at least two years follow-up for all patients. The trial is not powered to show a difference between group 2 and 1. Adding 15 % to allow for drop-outs, we aim to randomise a total of $18 + 18 + 9 = 45$ patients in a 2:2:1 ratio.

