8.5 Statistical Analysis

8.5.1 Primary analysis

- Primary variable: Overall survival at 2 years from randomization
- Assessment: From the electronic medical records (EPJ)
- Metric: Hazard ratio
- When the last recruited patient has reached two years follow-up or censor.

The primary analysis will be done by Cox regression with treatment group as covariate, adjusted for stratification factors in the randomization.

Primary population: By intention-to-treat (ITT), i.e. all randomized patients regardless of protocol adherence.

The treatment effect will be presented as hazard ratios between the two treatment groups and the standard of care group, in addition to 95% confidence intervals.

The null hypothesis to be tested is that there is no difference between the treatment groups on overall survival after 2 year. If the null hypothesis is rejected on a 5% significance level, the pairwise treatment group's differences will be tested on the 5% level with the family-wise error rate sustained by the closed test principle.

There will be no handling of missing values. All patients will be followed-up until 2 years or death of any reason. Patients lost to follow-up will be censored at time of last observation, and handled accordingly.

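### The single power of 0.80 in section 8.1 is not labelled as per comparison or joint, and at the stated 16/16/7 the analysis in 8.5.1 delivers it on neither reading

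*Protocol*

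**What the plan says.** Section 8.1 of the protocol assumes two-year survival of 30% on standard care, 75% with HAI and 90% with transplantation. The calculation is stated as: "For a two-sided parallel-group test of proportions to answer both questions with a power of 0.80 and an alpha of 0.05". Two requirements follow. For HAI: "this will require 16 completed patients per group 3 and 2 to show superiority for HAI over standard care". For transplantation: "An additional 7 patients is needed in the transplant group (1) to show superiority over standard care group (3), bringing the total to 39 patients". The drop-out allowance of 15% then brings the number randomised to 18 + 18 + 9 = 45.

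Section 8.5.1 uses a different method. The primary analysis is a Cox regression in all randomised patients, adjusted for the stratification factors. A global null hypothesis of no difference among the groups is tested first. Then: "If the null hypothesis is rejected on a 5% significance level, the pairwise treatment group's differences will be tested on the 5% level", under the closed test principle. Section 8.5.1 does not require both pairwise tests to succeed.

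**The concern.** One power figure is attached to two comparisons, and the sentence can be read in two ways: 0.80 for each comparison, or 0.80 for succeeding on both. The figure also belongs to a test of proportions, which is not the test that decides the trial.

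A reader of section 8.1 will take 0.80 as the chance that the trial does what it sets out to do if the planned effects are real. If the planned analysis does not deliver that figure on either reading, the prospects of a small trial are overstated, and a non-significant HAI or transplant result will be judged against the wrong power.

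**Working it through.** **Inputs.** Section 8.1: survival 0.30, 0.75 and 0.90; two-sided alpha 0.05; power 0.80; 16/16/7 completed; 18/18/9 randomised. Section 8.5.1: Cox regression, global test at 5%, then pairwise tests at 5%. Assumptions not in the protocol: exponential survival, censoring at two years, no covariate adjustment, the log-rank test standing for the Cox score test, and (last scenario only) 15% of patients censored early.

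**1. Reproducing 16 and 7.** The unpooled formula with equal groups is n per arm = (1.960 + 0.842)² × [p₁(1−p₁) + p₂(1−p₂)] / (p₂−p₁)².
- HAI v control: 7.849 × (0.21 + 0.1875) / 0.45² = 15.41, rounded up to 16.
- Transplant v control: 7.849 × (0.21 + 0.09) / 0.60² = 6.54, rounded up to 7.

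Both printed numbers are recovered, each from a stand-alone two-group calculation.

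**2. Joint power on that same formula.** The 7 transplant patients are compared with 16 controls, not 7.
- HAI: SE = √(0.21/16 + 0.1875/16) = 0.1576; power = Φ(0.45/0.1576 − 1.960) = 0.815.
- Transplant: SE = √(0.21/16 + 0.09/7) = 0.1612; power = Φ(0.60/0.1612 − 1.960) = 0.961.
- Correlation through the shared control arm: (0.21/16) / (0.1576 × 0.1612) = 0.52.
- Both, from the bivariate normal: 0.799.

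So on its own formula the printed 0.80 holds even as a joint figure.

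**3. The approximation is optimistic.** At 16/16/7 the pooled normal test gives HAI 0.745, transplant 0.834 and both 0.67. Exact enumeration of the three binomial counts with the chi-square test gives HAI 0.758, transplant 0.840 and both 0.680. Exact enumeration with the unpooled Wald test gives 0.771, 0.899 and 0.710.

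**4. Power under the 8.5.1 rule.** The log-rank column is simulated (20,000 runs). The chi-square column is exact and uses the same rule of a global test, then pairs. A dash means not computed.

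| Setting | Power | Log-rank | Chi-square |
|---|---|---|---|
| 16/16/7 | HAI without / with global test | 0.77 / 0.75 | 0.76 / 0.74 |
| | Transplant without / with | 0.80 / 0.76 | 0.84 / 0.80 |
| | Both | 0.66 | 0.68 |
| 18/18/9, no loss | HAI without / with | 0.82 / 0.81 | 0.84 / 0.82 |
| | Transplant without / with | 0.89 / 0.86 | 0.91 / 0.87 |
| | Both | 0.75 | 0.78 |
| 18/18/9, 15% censored early | HAI without / with | 0.78 / 0.77 | – |
| | Transplant without / with | 0.86 / 0.83 | – |
| | Both | 0.71 | – |

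Separate runs of the log-rank simulation put the joint figure at 0.65 to 0.66, 0.75 to 0.76 and 0.70 to 0.72 in the three settings. A Cox likelihood-ratio test for the pairs gives 0.69, 0.76 and 0.73.

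**5. What the global test costs.** To three decimals it takes nothing from the joint power: 0.680 with and without it at 16/16/7, and 0.779 with and without it at 18/18/9 (exact chi-square). It takes one to two points from HAI and three to four from transplant.

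**6. Power for at least one comparison through the global test** (exact chi-square). At 16/16/7: 0.740 + 0.798 − 0.680 = 0.858. At 18/18/9: 0.818 + 0.873 − 0.779 = 0.912.

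**The case against.** The strongest defence is that the 0.80 is correct on the protocol's own terms. Step 2 gives a joint power of 0.799, so even the stricter reading is met by the formula used. This stands, and it rules out a tempting inference: that sizing the comparisons separately must push the joint power down to roughly 0.64 to 0.69. That would follow only if each comparison had exactly 0.80, whereas transplant has 0.96 on this formula because it borrows the larger control arm. The shortfall comes from the optimistic unpooled approximation and from deciding by Cox regression instead of a test of proportions.

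A second defence is that the sentence may simply mean 0.80 for each comparison, since section 8.5.1 sets no requirement of joint success. That reading is fair, and at 18/18/9 with nobody lost both comparisons meet it. At the stated 16/16/7, HAI does not: 0.74 to 0.75 through the global test, and 0.76 to 0.77 without it.

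A reader might also blame the global test. The calculation does not support that for the joint figure (step 5). The global test would cost HAI more if transplantation did worse than planned, but the protocol contains no such scenario, and lower power under a smaller effect is not an error in section 8.1.

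Finally, 0.65 is the low end for 39 patients. Section 8.5.1 analyses all 45 randomised and censors those lost, so the 45-patient figures matter as much.

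**Conclusion.** The point holds as a matter of labelling and of the method behind the figure. Section 8.1 gives one power for two comparisons without saying what it refers to, and bases it on a test that section 8.5.1 does not use. At the stated 39 patients the planned analysis reaches 0.80 neither for HAI alone nor for both, and the joint figure is 0.65 to 0.68, or about 0.71 at most across the other approximate tests tried. At 45 patients with no loss each comparison is above 0.80, but both together are at 0.75 to 0.78. With 15% censored early, HAI falls just below 0.80 and both together to 0.70 to 0.73.

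It would be too strong to say that one trial in three fails on at least one comparison. That matches 39 patients only; at 45 it is roughly 22% to 30%. It would also be wrong to say that the trial is sized for success on either comparison: that power is about 0.86 to 0.91, and the derivation of 16 and 7 shows that each comparison was sized on its own.

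The figures rest on the planned survival rates, and those for log-rank and Cox also on exponential survival and no covariate adjustment. The early-censoring scenario is an assumption about how the 15% drop-out would act.

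**What to change.** In section 8.1, replace the single 0.80 with three figures computed under the 8.5.1 rule (global test, then pairwise): HAI v control, transplant v control, and both. Give them at 39 and at 45 patients, name the test and the survival assumption, and state the drop-out assumption used. On the calculations above these would be about 0.75, 0.76 to 0.80 and 0.65 to 0.68 at 16/16/7. At 18/18/9 with no loss they would be about 0.81, 0.86 to 0.87 and 0.75 to 0.78. With 15% censored early they would be about 0.77 to 0.78, 0.83 and 0.70 to 0.73.

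Add one sentence saying that the trial is sized for each comparison separately and not for joint success.

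The number of patients, the primary test and the closed test procedure stay as they are. The only cost is a less favourable printed figure.

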8.2 Randomization

8.2.1 Allocation-sequence generation

Randomized lists are generated for three groups in *Excalibur 1* in a 1:1:1 distribution and with a variable but unknown block-size of 3 or 6. Further, lists are generated for two groups in *Excalibur 2* in a 1:1 distribution. These will be generated and stored by personell not participating in the trial, and in offices physically removed from the clinical facilities.

8.2.2 Randomization and allocation procedures

A computer generated random sequence is generated with three groups for *Excalibur 1* and two groups for *Excalibur 2*. Randomization is blocked with a variable and unknown block-size of 2-6. Allocation is by phone to a centralized office physically removed from the clinical premises, or by web and performed after inclusion is judged appropriate and the patient has consented. For patients who are switched to 2nd line chemotherapy, randomization can only be allowed prior to first evaluation on 2nd line chemotherapy regimen.

Patients will be approached, informed and consented by study group members (surgeons or oncologists).

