Objectives	Main study objective: To improve treatment outcome for patients with a heavy burden of colorectal liver metastases and progression on 1 st line chemotherapy. Key secondary objectives: To establish whether the favourable results obtained by use of hepatic artery infusion chemotherapy can be replicated outside of US single centre series.
Endpoints:	Overall Survival (OS) at two years Secondary endpoints: Progression-free survival, overall survival at 5 years, resection/transplantation rate, quality of life.
Study Design:	Three-armed, two-sided, open label, parallel-group, single center, phase II trial.

Main Inclusion Criteria:	
– Multiple colorectal liver metastases (6 or more metastases)– Progression on 1st line chemotherapy
Main Exclusion Criteria	
– Extensive extrahepatic disease
Sample Size:	45 patients
Efficacy Assessments:	Overall survival, progression-free survival and resection rate
Safety Assessments:	Major adverse events/side-effects from chemotherapy and major complications following surgery.
Other Assessments:	Health economy assessment, quality-of-life

TABLE OF CONTENTS

CONTACT DETAILS	2
SIGNATURE PAGE	3
PROTOCOL SYNOPSIS	4
TABLE OF CONTENTS	6
1 INTRODUCTION	9
1.1 Background – Disease.....	9
1.2 Liver resections for Colorectal Liver metastases (CRLM).....	9
1.3 The grey zone.....	10
1.4 Systemic chemotherapy for CRLM.....	10
1.5 Liver transplant for CRLM.....	10
1.6 Hepatic artery infusion (HAI) chemotherapy for CRLM.....	10
1.7 Optimal treatment for patients with CRLM in the grey zone.....	11
1.8 Rationale for the Study and Purpose.....	11
1.9 Research hypothesis.....	11
2 STUDY OBJECTIVES AND RELATED ENDPOINTS	12
3 OVERALL STUDY DESIGN/OVERVIEW OF DESIGN	13
4 STUDY POPULATION	13
4.1 Selection of Study Population.....	13
4.2 Number of Patients.....	14
4.3 Inclusion and exclusion criteria.....	14
4.3.1 Inclusion Excalibur 1	14
4.3.2 Inclusion Excalibur 2	Feil! Bokmerke er ikke definert.
4.4 Exclusion Criteria.....	14
4.4.1 Exclusion.....	Feil! Bokmerke er ikke definert.
5 TREATMENT	15
5.1 Technical procedures.....	15
5.1.1 Second line systemic chemotherapy.....	15
5.1.2 Liver transplantation.....	15
5.1.3 Hepatic Artery infusion (HAI).....	16
5.1.4 Surgical procedure.....	16
5.2 Drug Accountability - IMP.....	20
5.3 Drug Labeling.....	20
5.4 Subject Numbering, different arms of the study.....	21
5.5 Schedule of events.....	21
5.6 By Visit.....	23

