4. Non-curable pulmonary or peritoneal metastases, non-regional lymph-nodes, or local recurrence on PET/CT scan, and on CT or MRI thorax/abdomen/pelvis dated within 6 weeks prior to the trial hospital MDT meeting.
5. Patients with known intolerance or allergy to any ingredient of the IMP to be used as standard therapy for that patient must be excluded
6. Breastfeeding women must be excluded
7. Patients with a psychiatric condition that makes participation in the trial impossible or unethical
8. Patients in a poor nutritional state, those with depressed bone marrow function or those with potentially serious infections must be excluded.
9. Any other reason why, in the opinion of the investigators, the patient should not participate.

Exclusion Excalibur 1

Any of the following will preclude inclusion into Excalibur 1 (but not into Excalibur 2)

1. BRAF positivity
2. Any sign of extra-hepatic metastatic disease or local recurrence on PET/CT scan, and on CT or MRI thorax/abdomen/pelvis dated within 6 weeks prior to the trial hospital MDT meeting (exception allowed for ≤ 3 resectable lung lesions all ≤ 15 mm).
3. Liver lesion >10 cm
4. Patient BMI > 30
5. Any previous non colorectal malignancy within latest five years
6. Age ≥ 70 years

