5.5 Schedule of events

- Identification
 - Patients are identified from referrals or during MDT-meetings by surgeon or oncologist.
 - A trial specific MDT evaluation of liver metastases and resectability is performed.
 - Following this MDT-meeting, the patient is invited for out-patient visit within 10 days.
 - If no updated high-quality thoracic/abdominal CT and MR scan is available (No older than 4 weeks by date of out-patient visit), these are booked.
- At out patient clinic:
 - Eligibility for *Excalibur* 1 or 2 is assessed.
 - In house review of new images if applicable.
 - Eligible patients receive written and oral information about the trial and risks pertaining to HAI-catheter insertion/transplant/systemic chemotherapy
 - Measurement of CEA and standard blood chemistry
 - If patient consents:
 - Baseline QoL survey (C30) and EQ5D questionnaire is completed
 - Patient's latest CT or MRI scans are referred to next MDT meeting for designation of three target lesions for RECIST evaluation
 - Availability of mutation status is confirmed. If mutation status is not already performed, this is ordered from pathology lab.
 - Decision of eligibility for *Excalibur* 1 or 2 is decided by two trial investigators. If a patient is found to be eligibility for *Excalibur* 1 a member of transplant team will concur and provide specific information about transplants.
 - If a patient has begun or is planned for 2nd line chemotherapy, the randomization MUST take place before any evaluation of 2nd line treatment effect, i.e imaging (CT/MR). (PET for evaluation of extra hepatic disease is allowed). The choice of drugs for 2nd line chemotherapy must be decided on prior to randomization.
 - Inclusion is confirmed
 - Patient card
 - The following appointments are booked within two weeks:
 - A PET scan following 4 week chemo abstinence. If the patient has recently received systemic chemotherapy, a 4 week chemo abstinence must be ensured and randomization may need to be somewhat delayed.
 - Patients eligible for *Excalibur* 1 for individual assessment by transplant team
 - An operation theatre for insertion of HAI-pump catheter at four weeks from inclusion
- PI meeting two weeks following inclusion:
 - Documents, inclusion details, transplant assessment and PET results are reviewed

- If satisfactory, a web-based randomization is performed.
- All patients:

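### Block sizes described as unknown are printed in the protocol, are small and are not reconciled between sections 8.2.1 and 8.2.2, so in this open, single-centre trial the enrolling team can guess the next arm well above chance

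*Protocol*

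**What the plan says.** **Block sizes.** Protocol section 8.2.1 describes the three-group, 1:1:1 list for Excalibur 1 "with a variable but unknown block-size of 3 or 6". For the other sub-trial it adds only "Further, lists are generated for two groups in *Excalibur 2* in a 1:1 distribution", with no block size. Section 8.2.2 covers both sub-trials together: "Randomization is blocked with a variable and unknown block-size of 2-6".

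**Concealment.** Section 8.2.1 has the lists made and kept off site by people outside the trial. Section 8.2.2 has allocation released centrally, by phone or web, after consent.

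**Visibility.** The synopsis describes a "Three-armed, two-sided, open label, parallel-group, single center, phase II trial". Under section 4.1, HAI, resection and transplantation are all done at the one hospital.

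**Discretion before allocation.** Section 8.2.2 has study group surgeons and oncologists enrol the patients. Under section 5.5, eligibility for Excalibur 1 or 2 "is decided by two trial investigators". A PI meeting two weeks after inclusion then reviews the case: "If satisfactory, a web-based randomization is performed". The last general exclusion in section 4.3 is open-ended: "Any other reason why, in the opinion of the investigators, the patient should not participate".

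**Strata.** Section 3 mentions stratification by age and primary tumour status, and section 8.5.1 adjusts for stratification factors. Section 8.2 names none.

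**The concern.** A block size printed in the protocol is not unknown to the people who work from that protocol. Keeping the list off site stops anyone reading it. It does not stop someone who has seen every earlier allocation from working out what is probably left in the current block, and the smaller the block, the easier that is.

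What is at stake is selection before randomisation. If the next arm can be guessed, the timing of a borderline patient, or the use of the open-ended exclusion, can depend on that guess, even without intent. Section 10 records that the investigators firmly believe both interventions do more good than harm. That is no evidence of steering, but allocation concealment exists so that such a belief cannot matter.

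The planned arms hold 9 to 18 patients (section 8.1), so a few selectively timed patients could move a hazard ratio. Intention-to-treat analysis does not help, because the selection comes before randomisation. Cox adjustment for the stratification factors cannot remove selection on prognosis that was never recorded.

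**Working it through.** The plan derives no figure for block size, so there is none to reproduce. The checks are whether the two statements fit together, and how predictable the lists are.

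**1. Which sizes are possible.** A balanced block must be a multiple of the number of arms. Of the sizes 2, 3, 4, 5 and 6:
- at 1:1:1, 3 and 6 work; 2, 4 and 5 do not;
- at 1:1, 2, 4 and 6 work; 3 and 5 do not.

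Size 5 fits neither list. The range in 8.2.2 agrees with 8.2.1 only if it means 3/6 for one list and 2/4/6 for the other, which the text does not say.

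**2. List lengths (implied, not stated).** Section 8.1 plans 18 + 18 + 9 = 45. The 9 transplant patients can come only from Excalibur 1, so at 1:1:1 that list has 3 × 9 = 27 patients. The other two arms then need 18 − 9 = 9 each from Excalibur 2, which gives 2 × 9 = 18.

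**3. How a guess is formed.** Assume the observer knows the printed sizes, treats them as equally likely, and has seen all past allocations.
- *Excalibur 2, sizes 2/4/6.* After the first patient gets arm A, each size is still equally likely. The chance that B is next is (1 + 2/3 + 3/5)/3 = 0.756.
- *Excalibur 1, sizes 3/6.* Suppose the first two patients get A then B. The likelihood is 1/3 × 1/2 = 1/6 for a block of 3 and 2/6 × 2/5 = 2/15 for a block of 6. The block is therefore of size 3 with probability (1/6)/(1/6 + 2/15) = 5/9. The chance that C is next is 5/9 × 1 + 4/9 × 2/4 = 7/9 = 0.78.

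**4. Whole lists.** This rule was applied to 20,000 simulated lists per scenario, guessing the most probable arm each time. As a check on the method, fixed blocks have exact answers: (1/3 + 1/2 + 1)/3 = 0.611 for size 3 and (1/2 + 1)/2 = 0.750 for size 2. The simulation returned 0.611 and 0.750.

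| Scenario | Best guess right | By chance | Next arm certain | One arm at 80% or more |
|---|---|---|---|---|
| Excalibur 1, sizes 3/6, n = 27 | 57.2% | 33.3% | 8.2% (2.2 patients) | 24.8% |
| Excalibur 2, sizes 2/4/6, n = 18 | 69.5% | 50% | 3.6% (0.65 patients) | 47.6% |
| Excalibur 1, four equal strata of 7 (assumed) | 53.6% | 33.3% | 5.6% | 14.9% |
| Excalibur 2, four equal strata of 5 (assumed) | 65.1% | 50% | 1.9% | 29.2% |

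Stratum sizes are 27/4 and 18/4, rounded up. If Excalibur 2 used only two of the sizes 2, 4 and 6, the guess would be right 68% to 72% of the time, with 6% to 10% of allocations certain.

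**5. What larger blocks would do.** In a separate run of 2,000 unstratified lists per scenario, with sizes still known, blocks of 6/9 in Excalibur 1 gave 53% correct and blocks of 6/8/10 in Excalibur 2 gave 65%. The share of allocations with one arm at 75% or more fell from 33% to 18% and from 59% to 27%. The price is imbalance. With four assumed strata, lists with an arm difference of 3 or more rise from 19% to 35% in Excalibur 1, and lists with a difference of 4 or more rise from 12% to 26% in Excalibur 2.

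**The case against.** - **Allocation is central and the lists are off site.** True, and this protects the list itself. It does not prevent inference from past allocations.
- **The range 2-6 can be a union of feasible sizes.** This stands. A reader might infer that 8.2.2 cannot be carried out because it contains impossible sizes. The text gives a range for two lists at once and does not say that every whole number is used on each, so that inference is not supported. What remains is that the text leaves the reader to guess the scheme.
- **Little is certain.** This stands. Both sections say that the size varies, so the fixed-block results (33% of allocations certain with size 3, 50% with size 2) describe a design that the protocol does not have.
- **Strata would lower predictability.** Also fair. Sections 3 and 8.5.1 suggest strata and section 8.2 names none, so the unstratified figures are the upper end of a range.
- **Steering has limited room.** Largely stands. The Excalibur 1 exclusions are mostly objective (BRAF, lesion size, BMI, age), and a transplant-team member must concur. The review at the PI meeting concerns documents, transplant assessment and PET results. Theatre is booked for four weeks from inclusion, and randomisation must precede the first evaluation on second-line treatment. Moving patients between lists is therefore the weaker route; timing and the open-ended exclusion are the more plausible ones.
- **Small blocks are defensible at this sample size.** This stands too. Larger blocks trade predictability for imbalance, so the protocol need not be faulted for choosing small ones, only for publishing them.

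**Conclusion.** The point holds as a correctable weakness in allocation concealment. The sizes are published under the label unknown, the two sections are not reconciled, and an enrolling team that sees past allocations could guess the next arm about 57% of the time against 33% in Excalibur 1, and about 70% against 50% in Excalibur 2. Certain allocations are few, about 8% and 4%. With four equal strata the guess rates are about 54% and 65%, with about 6% and 2% certain.

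These figures assume equally likely sizes, full knowledge of past allocations and the implied 27/18 split.

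A reader might go further and infer that the team can usually know the next arm, or that patients will be steered. The documents support neither: predictability is well above chance but mostly short of certainty, and nothing shows intent. The effect on the survival comparison has not been quantified.

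**What to change.** 1. Delete the block sizes from sections 8.2.1 and 8.2.2. For each sub-trial, state only the allocation ratio, any strata, and that randomly varying blocks are used.
2. Hold the sizes in a restricted file with the off-site list holder. That person chooses them, weighing predictability against imbalance; avoiding the smallest blocks is optional.
3. If lists with the published sizes already exist, regenerate the unused part with undisclosed sizes.
4. Record the Excalibur 1/2 assignment and the final eligibility decision in the web system before the allocation is released.

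The cost is a change of wording, a regenerated list and a logging step in a system already planned. If larger blocks are chosen, the arms may end unequal by a few patients.
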